### **7.3.2 Dose Modification, Interruption or Discontinuation for Adverse Events**

The investigator and/or DSMB have the authority to reduce study medication dosage or discontinue study medication in a patient if situations develop that, in the opinion of the investigator or DSMB, would compromise the patient's safety or successful participation in the study (see Section 4.3 *Data Safety Monitoring Board* and Section 7.4 *Patient Discontinuation Criteria*). In particular, modifications in dosage or discontinuation of treatment will be instituted if any of the situations below apply.

#### **HEPATOBILIARY GUIDELINES**

##### **Dose Modification Based on Hepatobiliary Adverse Events**

If a patient matches the criteria referred to as "Hy's law case" according to the European Association for the Study of the Liver (EASL) Clinical Practice Guidelines on Drug-induced Liver Injury (EASL 2019) and the FDA Guidance for Industry Drug-Induced Liver Injury Premarketing Clinical Evaluation (FDA 2009) or shows comparable signs of liver toxicity, irrespective of origin, treatment must be permanently discontinued and no re-challenge will be allowed.

Upon the investigator's discretion study medication will be discontinued permanently if a patient experiences any CTCAE Grade 3 or Grade 4 hepatobiliary AE (see Appendix 3

*Common Terminology Criteria for Adverse Events, Hepatobiliary Disorders),* regardless of relationship to study drug.

### **Biochemical Hepatobiliary Guidelines**

Note: The toxicity “levels” described below are different and separate from CTCAE “grades”. The toxicity levels do NOT correlate to CTCAE grades nor should they be used for grading AEs.

If aminotransferase elevations are accompanied by clinical symptoms of liver injury (such as nausea, vomiting, abdominal pain, fever, jaundice, lethargy, flu-like symptoms), increases in bilirubin  $\geq 2 \times$  ULN, study drug will be discontinued, the event will be reported to the DSMB by the sponsor (or its designee) immediately upon notification and the patient referred to a hepatologist for further work up.

#### Level 4 Hepatotoxicity

Level 4 Hepatotoxicity is defined as follows:

- ALT or AST levels reach  $\geq 10 \times$  ULN at 1 single time point. Patients should be referred to a hepatologist or gastroenterologist for further work up.
- In symptomatic patients, ALT  $> 5 \times$  ULN AND total bilirubin  $> 2 \times$  ULN on 2 separate occasions and at least 7 days apart.
- AP is  $> 5 \times$  ULN on 2 separate occasions and at least 7 days apart.
- Total bilirubin is  $> 2 \times$  ULN on 2 separate occasions and at least 7 days apart in the absence of Gilbert’s syndrome or haemolysis.

Patients who experience confirmed Level 4 Hepatotoxicity will immediately interrupt study medication. Patients will return to the study site weekly or sooner if clinically indicated until resolution. Any Level 4 Hepatotoxicity will be reported to the DSMB by the sponsor (or its designee) immediately upon notification.

Following evaluation by a hepatologist, a patient may resume lomitapide treatment if the Level 4 Hepatotoxicity is resolved, and in the opinion of the investigator, DSMB and sponsor, the benefit of treatment justifies any risk of recurrent toxicity.

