#### Dose Reduction and Re-challenge

If a dose reduction is required, dosage will either be reduced to the previous tolerated dose or to an intermediate dose. Please note that only down-titrations to intermediate doses are allowed, dose escalations need to follow the guidance provided in Table 2. After resolution of the cause for dose reduction, patients may be re-challenged after a minimum period of 4 weeks following dose reduction with prior doses in stepwise increments based on dose escalation guidelines, but may not exceed the MTD established during the Efficacy Phase until

Week 24±3 days, after which further increase is only possible if patients have crossed into the next age category or eligibility for exceptional dose escalation as described above is met.

If the investigator determines that a patient is not tolerating any particular dose (per specified criterion), the investigator may request a dose reduction or a hold on the current dose until the next scheduled visit. Once the patient has stabilised on the reduced dose, the dose can be increased back to the next step again, and the patient may progress through subsequent dose increases at a minimum of 4-week intervals. If the patient does not tolerate the re-challenge dose, then the MTD is considered the reduced dose and will be the highest dose allowed for the remainder of the study.

Weeks 0 through 24±3 days establish the MTD, Week 20±3 days is the last visit that the lomitapide dose can be increased, except when there has been a down-titration at/or after Week 16±3 days. Re-challenging will depend on the assessment of safety and tolerability criteria and the LDL-C value relative to the LDL-C goal of <135 mg/dL (3.5 mmol/L) and is at the discretion of the investigator except for Hy's law cases or comparable signs of liver toxicity, irrespective of origin, in which no re-challenge will be allowed (see Section 7.4 *Patient Discontinuation Criteria*).

The study medication can be escalated as a re-challenge dose during an unscheduled visit after the investigator consults with the study medical monitor, but any additional dose escalations, i.e., dose titration, must be made during a completed scheduled visit. In addition, a re-challenge with lomitapide will not be performed if the LDL-C is below the target threshold while the patient was receiving the reduced dose.

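### Three safety rules are each stated in two unreconciled ways: when to stop drug for combined ALT and bilirubin elevation, whether Type 3/4 NASH ends participation, and which weight loss triggers dietitian referral

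*Protocol*

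**What the plan says.** **Liver stopping rule.** Section 7.3.2 begins with a permanent stop for a Hy's law case or a patient showing "comparable signs of liver toxicity, irrespective of origin, treatment must be permanently discontinued and no re-challenge will be allowed". Section 7.3.1 repeats the bar as an exception to investigator discretion, for Hy's "law cases or comparable signs of liver toxicity, irrespective of origin, in which no re-challenge will be allowed", and Section 7.4 lists it as mandatory. The opening paragraph of the Biochemical Hepatobiliary Guidelines then says that, when aminotransferase elevations come with clinical symptoms of liver injury and bilirubin of at least 2 × ULN, "study drug will be discontinued, the event will be reported to the DSMB by the sponsor (or its designee) immediately upon notification". It asks for no repeat reading.

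The Level 4 text includes symptomatic patients with ALT above 5 × ULN and total bilirubin above 2 × ULN, but only on two occasions at least 7 days apart. Its action is: "Patients who experience confirmed Level 4 Hepatotoxicity will immediately interrupt study medication". After hepatologist evaluation, "a patient may resume lomitapide treatment if the Level 4 Hepatotoxicity is resolved", provided the investigator, DSMB and sponsor judge that benefit justifies the risk. Section 7.4 and the synopsis list Level 4 among reasons for which the investigator is able to withdraw a patient.

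**NASH.** The Histopathological Hepatobiliary Guidelines in Section 7.3.2 discontinue a patient with Type 3 or Type 4 NASH from the study. Section 7.4 and the synopsis put the same diagnosis in the list of optional reasons for withdrawal.

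**Weight.** Sections 2.6.3, 7.3.2 (Dose Modification Based on Weight Loss) and 8.6.1 send a child of normal or below-normal weight to the dietitian after a loss of more than 3% since the last visit. Section 8.1.1 (Physical Examination) uses more than 1.5 kg.

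**The concern.** Each rule tells a site what to do for one child, and each can be looked up in two places with different answers. For the liver rule, a site working only from the Level 4 text could wait for a second reading before acting, while a site working from the paragraph above it would stop at once. The classification also matters for the whole trial: under Section 4.3, permanent discontinuation for a Hy's law case or comparable toxicity obliges the DSMB to stop recruitment, whereas Level 4 on its own terms leads to interruption and possible resumption. For NASH, one site would withdraw a child whom another could keep in the study. For weight, the smallest children would be referred late under the kilogram trigger. These are clinical management rules, which belong in the protocol and would not be settled by a statistical analysis plan.

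**Working it through.** The protocol states no figure to reproduce. The check applies each rule to the same child.

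**1. Combined ALT and bilirubin elevation.** Case: symptomatic, ALT above 5 and below 10 × ULN, bilirubin above 2 × ULN, first reading.

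- Opening paragraph of the Biochemical Hepatobiliary Guidelines: met. Drug is discontinued, the DSMB informed and a hepatologist consulted. As printed, the sentence lacks a conjunction between symptoms and bilirubin ("fever, jaundice, lethargy, flu-like symptoms), increases in bilirubin"), but this child meets it whether the missing word is *and* or *or*, and a value above 2 satisfies at least 2.
- Level 4, single-reading criterion (ALT or AST at least 10 × ULN): not met.
- Level 4, symptomatic ALT-plus-bilirubin criterion: not met until a second reading at least 7 days later. The bilirubin-alone criterion has the same condition.
- Level 3 (ALT or AST at least 5 × ULN): also needs two readings at least 7 days apart.

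The delay is therefore 0 days if the opening paragraph is applied and at least 7 days if a site uses the Level definitions alone. The actions differ too (discontinue against interrupt), and no sentence says which prevails.

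After confirmation and resolution, the Level 4 text permits resumption. Sections 7.3.1, 7.3.2 (opening) and 7.4 forbid it if the case is Hy's law or comparable. The Level 4 sentence does not refer to that bar.

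Frequency, from the adult pivotal study in Section 2.6.3: ALT above 5 × ULN in 4 of 29 (4/29 = 13.8%), with 3 of the 4 reporting alcohol above the permitted amount; raised bilirubin in 0 of 29. The joint event was not seen.

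**2. Type 3/4 NASH.** Section 7.3.2: discontinued from the study. Section 7.4 and synopsis: investigator may withdraw. The two differ directly. The rule reaches only children who are biopsied; biopsy is to be considered after at least 6 months of ALT or AST at or above 3 × ULN, or at the investigator's discretion.

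**3. Weight-loss trigger.** Express 1.5 kg as a share of body weight, 1.5/W. Inclusion criterion 3 admits children from 15 kg.

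| Body weight | 1.5 kg as % of weight | 3% in kg |
|---|---|---|
| 15 kg | 1.5/15 = 10.0% | 0.45 |
| 30 kg | 1.5/30 = 5.0% | 0.90 |
| 50 kg | 1.5/50 = 3.0% | 1.50 |
| 70 kg | 1.5/70 = 2.1% | 2.10 |

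The triggers agree only at 1.5/0.03 = 50 kg. Below that, the kilogram rule is looser; above it, stricter.

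**The case against.** The best reply is that the liver text overlaps but does not contradict itself. The stop paragraph heads the guidelines, above all four Levels. Nothing under Level 4 tells a site to keep dosing while it waits, and a site can comply with both by stopping under the first and classifying under the second. Section 7.3.2 also states that "The investigator and/or DSMB have the authority to reduce study medication dosage or discontinue study medication in a patient if situations develop" which would compromise safety. On resumption, a permissive *may* does not displace a mandatory *must*. Level 4 also covers presentations that need a resumption route, such as an isolated alkaline phosphatase rise, and resumption needs a hepatologist and the DSMB. Section 2.6.3 adds that the algorithm rests on an approach used successfully in the adult study.

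Most of this stands, and it rules out three stronger readings that a reader might infer:

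- *That the protocol directs continued dosing, or allows re-challenge of Hy's law cases.* It does neither when read as a whole. It also gives no numeric Hy's law thresholds, so the documents cannot show which Level 4 cases are Hy's law.
- *That the stop paragraph contradicts Levels 1 and 2.* That requires reading the missing conjunction as *or*, and the word may have been lost when the PDF was read.
- *That leaving Grade 3 hepatobiliary events to the investigator's "discretion study medication will be discontinued permanently if a patient experiences any CTCAE Grade 3 or Grade 4 hepatobiliary AE" undercuts the Hy's law rule.* The mandatory rule is in the paragraph immediately before and limits the discretion.

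What the reply does not remove is the absence of a stated precedence, or the NASH and weight discrepancies. Those two are narrow: NASH depends on biopsy, and the weight trigger governs dietitian referral only, since the drug-stopping rule for weight loss is the same in Sections 7.3.2 and 8.1.1.

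**Conclusion.** The point holds as three unreconciled statements of safety rules, minor to moderate in weight and worth correcting because they concern children and cost little. (1) The liver rule has two timings for one presentation, 0 days or at least 7 days, and a resumption sentence without the exception stated elsewhere. Applying the stricter text resolves both, and the case should be rare if children resemble the 29 adults, which is an assumption. (2) Type 3/4 NASH is mandatory in one section and discretionary in two places. (3) The dietitian trigger differs by a factor of more than three for a 15 kg child (1.5 against 0.45 kg) and agrees only at 50 kg. The missing conjunction, the unnamed ALT/AST multiple, and the bilirubin boundary (at least 2 against above 2 × ULN) in the stop paragraph are points for the hepatologist to clarify, not demonstrated errors.

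**What to change.** 1. Under Level 4, state that the symptomatic ALT-plus-bilirubin criterion stops drug at the first reading and that the second reading serves only to classify the event. Limit the resumption sentence to cases other than Hy's law or comparable liver toxicity.
2. Move Type 3/4 NASH to the mandatory discontinuation list in Section 7.4 and the synopsis.
3. In Section 8.1.1, replace the 1.5 kg trigger with the 3% trigger used elsewhere.
4. At the same time, ask the hepatologist to settle the conjunction, the ALT/AST multiple and a single bilirubin boundary in the stop paragraph.

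The cost is a wording amendment with hepatologist sign-off, plus occasional drug holds for a first reading that does not confirm. No new visits, tests or patients are needed.

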#### Level 3 Hepatotoxicity

Level 3 Hepatotoxicity is defined as follows:

- Patients who experience ALT or AST  $\geq 5 \times$  ULN on 2 separate occasions and at least 7 days apart.

Patients who experience confirmed Level 3 Hepatotoxicity will immediately interrupt study medication. The patient will return to the clinic for repeat blood tests including AP, bilirubin and International normalised ratio (INR) every 7 days until the aminotransferase levels have fallen  $< 3 \times$  ULN. Once this occurs, study drug dosing may be resumed at the dose level below that associated with Level 3 Hepatotoxicity.

If this dose level is tolerated without elevation of ALT or AST  $> 3 \times$  ULN, then this dose will be defined as the MTD. If aminotransferases increase  $\geq 3 \times$  ULN further dose reduction or interruption may be necessary consistent with the guidance provided in this protocol.

Elevations in ALT or AST  $> 3 \times$  ULN that persist despite dose reduction or interruption for  $\geq 4$  weeks will be reported to the DSMB by the sponsor (or its designee) immediately upon notification. Patients will be referred to a hepatologist for further work up.

### Level 2 Hepatotoxicity

Level 2 Hepatotoxicity is defined as follows:

- Patients who experience ALT or AST 3.0 to 4.9 x ULN on 2 separate occasions and at least 7 days apart.

Patients who experience confirmed Level 2 Hepatotoxicity will have the dose of study medication reduced to the previous tolerated dose. The patient will return to the clinic for repeat blood tests including AP, bilirubin and INR every 7 days until the aminotransferase levels have fallen to <3 x ULN. Once this occurs, lomitapide dosing may be resumed at the dose level below that associated with Level 2 Hepatotoxicity.

If this dose level is tolerated without elevation of ALT or AST >3 x ULN, then this dose will be defined as the MTD. If aminotransferases increase >3 x ULN further dose reduction or interruption may be necessary consistent with the guidance provided in this protocol.

Elevations in ALT or AST >3 x ULN that persist despite dose interruption for  $\geq 4$  weeks will be reported to the DSMB by the sponsor (or its designee) immediately upon notification. Patients will be referred to a hepatologist for further work up.

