***Number of visits (study)***

There will be 23 visits from Screening through Follow-up:

- Screening: n = 1.
- Run-in Period: n = 2.
- Efficacy Phase: n = 7, every 4 weeks $\pm$ 3 days.
- Safety Phase including End of Treatment (EoT):
  - After Week 24 $\pm$ 3 days through Week 52 $\pm$ 3 days: n = 8, every 4 weeks $\pm$ 3 days.
  - After Week 56 $\pm$ 3 days through Week 104 $\pm$ 1 week: n = 4, every 12 weeks $\pm$ 1 week.
- Follow-up: n = 1.

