### 2.6.3 Known and Potential Risks

Inhibition of MTP is expected to cause accumulation of triglycerides in intestinal mucosa and hepatocytes, and malabsorption of fat and fat-soluble vitamins from the diet. Major histological findings from non-clinical toxicological experiments showed increased incidences of lipid vacuolation in small intestinal mucosal epithelium and hepatocytes.

However, increased incidences of liver and small intestine tumours in mice were not noted in clinical studies and may not be expected to occur in clinical use due to the lack of genotoxicity, immunotoxicity, or other cellular injury associated with high levels of lomitapide exposure. In addition, unphysiological factors in the non-clinical experiments such as vitamin E depletion and severe hypocholesterolaemia will be prevented by administering dietary supplements (see Section 6.3 *Dietary Supplements*) and by closely monitoring LDL-C levels (see Section 1.2 *Flow Chart of Study and Follow-up*).

In the pivotal phase III study, 10 of 29 patients experienced elevations of ALT and/or AST  $>3 \times$  ULN once or more during the study. Four of these patients exhibited ALT increases  $>5 \times$  ULN. No patient discontinued treatment permanently due to LFT elevations and all elevations were managed either by dose reduction or temporary interruption of lomitapide as per protocol. Of note, 3 of 4 patients with LFT elevations  $>5 \times$  ULN reported consuming quantities of alcohol higher than those allowed per protocol. No patient experienced elevations in bilirubin or AP levels (Cuchel, Meagher et al. 2013).

During the extension study, 4 of 19 (21.1%) patients experienced a  $\geq 5 \times$  ULN increase in ALT or AST. Increases  $\geq 5 \times$  ULN were typically associated with concomitant use of CYP 3A4 inhibitors or excess alcohol use. These events were successfully managed by discontinuing offending medication, lomitapide dose reductions or suspension, and reintroduction of lomitapide after normalisation of transaminases (Blom, Averna et al. 2017).

Management of elevated hepatic aminotransferases in this study is carefully specified by an algorithm in Section 7.3.2 *Dose Modification, Interruption or Discontinuation for Adverse Events*. In addition, an independent DSMB will provide oversight of patient safety (see Section 4.3 *Data Safety Monitoring Board*).

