### Level 1 Hepatotoxicity

Level 1 Hepatotoxicity is defined as follows:

- Patients who experience ALT or AST 1.1 to 2.9 x ULN.

No dose modification will be required.

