## **Considerations for Liver Biopsy and Histopathological Guidelines**

### Considerations for Liver Biopsy

A percutaneous liver biopsy should be considered for persistent Level 2 Hepatotoxicity defined as AST or ALT  $\geq 3$  x ULN for  $\geq 6$  months but can also be performed at the discretion of the investigator.

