### **11.5.2    *Reporting of Adverse Events of Special Interest***

All AESIs (see Section 11.1.6 *Adverse Events of Special Interest*) should be reported within 15 calendar days. The investigator should complete the AESI report form in the investigator site file and send the initial AESI report to the Pharmacovigilance Department at **[contact]**.

The minimum information required for the initial AESI report is:

- Identifiable patient
- Identifiable reporter
- Investigational product
- Description of the event

If relevant information is missing at the time of the initial AESI report, the reporter should provide it in follow-up AESI report(s) upon availability. The follow-up report should contain new, updated or corrected information. It should further describe whether the event has resolved or

continues, and if and how it was treated including documentation of all supportive actions taken.

All AESIs will be diligently followed-up using specialised query follow-up forms. They will be systematically collected, reviewed, and discussed in relevant safety aggregate reports. AESIs will be identified as potential signals that will be reviewed during routine monthly signal detection activities.

Specific hepatic and gastro-intestinal abnormalities, hepatic fibrosis, primary hepatic tumours, small bowel/intestinal or pancreatic tumours and major congenital abnormalities will be reported expeditedly.

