### **12.3.6 Planned Analysis for Safety Endpoints**

Safety will be assessed using the SAF Population, including all patients who receive any amount of study medication, and will be based on evaluation of AEs, laboratory data, vital signs and physical examination findings, height, weight, BSA and BMI, ECG, echocardiography (if available) and hepatic fat. Safety data summary statistics will be presented overall and by age group.

Adverse events will be coded using the Medical Dictionary for Regulatory Activities (MedDRA) for purposes of summarisation. All AEs occurring during the study will be included in by-patient data listings and will be summarised overall and by age group. Events leading to death, SAEs, and events resulting in study discontinuation will be summarised. Adverse events of special interest, such as hepatobiliary AEs and hepatotoxicity of different levels, will be summarised (see Section 11.1.6 *Adverse Events of Special Interest*).

Reported clinical laboratory results and changes from Baseline will be summarised using descriptive statistics overall and by age group. Shift tables and summaries of potentially clinically significant findings will be presented. Reported values and changes from Baseline for vital signs, ECG findings, and echocardiography (if available) will be summarised by time point overall and by age group. For lipid accumulation in the liver, the number and percentage of patients with liver fat content ≤10%, >10% and ≤20%, and >20% will be summarised overall and by age group. Changes from Baseline over time will be presented in shift tables for ECG results, echocardiography (if available) and lipid accumulation in the liver.

To assess sexual maturation, changes from Baseline in Tanner staging results will be presented in shift tables and graphically.

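### A patient with one ALT/AST value of 3.0–4.9 and another of 5.0–9.9 × ULN falls between Level 2 and Level 3 hepatotoxicity, so no dose action or weekly retest is required

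*Protocol*

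**What the plan says.** All the level definitions are in Protocol Section 7.3.2, under the biochemical hepatobiliary guidelines.

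- **Level 4**, transaminase criterion: a single ALT or AST value of at least 10 × ULN. Its other criteria need raised bilirubin or alkaline phosphatase.
- **Level 3**: ALT or AST of at least 5 × "ULN on 2 separate occasions and at least 7 days apart". Study drug is interrupted and bloods are repeated every 7 days.
- **Level 2**: "Patients who experience ALT or AST 3.0 to 4.9 x ULN on 2 separate occasions and at least 7 days apart". The dose goes back to the previous tolerated step and bloods are repeated every 7 days.
- **Level 1**: ALT or AST of 1.1 to 2.9 × ULN. "No dose modification will be required".

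The biopsy paragraph of the same section refers to "persistent Level 2 Hepatotoxicity defined as AST or ALT" of at least 3 × ULN for 6 months or more, with no upper limit. Section 12.3.6 states that adverse events of special interest (AESIs), "such as hepatobiliary AEs and hepatotoxicity of different levels, will be summarised". The synopsis (Number of visits) sets visits every 4 weeks up to Week 56 and then "n = 4, every 12 weeks". On the expected risk, Section 2.6.3 reports that 10 of 29 adults in the pivotal study exceeded 3 × ULN on ALT and/or AST. It adds: "Four of these patients exhibited ALT increases" above 5 × ULN.

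**The concern.** The cap of 4.9 in Level 2 applies to both draws, and the floor of 5 in Level 3 also applies to both. A pair with one value on each side of 5 × ULN therefore belongs to neither level.

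This inverts the intended ordering. Two values of 4.0 require a dose reduction and weekly monitoring; a rise from 4.5 to 9.0 requires nothing. If some other draw lay between 1.1 and 2.9 × ULN, the only level the patient meets is Level 1, which calls for no dose change.

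Liver injury is a main known risk of this drug and the patients are children. Section 2.6.3 relies on the Section 7.3.2 algorithm as the way raised aminotransferases are managed. The gap also reaches the analysis: on these definitions, a tabulation by level omits such a patient or shows Level 1 until a further value of at least 3 × ULN arrives.

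**Working it through.** **Scope.** Two draws of the same enzyme, at least 7 days apart, in a patient without symptoms of liver injury and with normal bilirubin and alkaline phosphatase. Outside this scope other rules apply: Section 7.3.2 stops the drug when the elevation comes with symptoms or bilirubin of at least 2 × ULN.

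**1. Classify every pair.** Take values from 3.0 to 9.9 × ULN in steps of 0.1: 20 values in 3.0–4.9, 50 values in 5.0–9.9, and 70 × 70 = 4,900 ordered pairs.

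| Pair | Level in current text | Pairs |
|---|---|---|
| both 3.0–4.9 | Level 2 | 20 × 20 = 400 |
| both 5.0–9.9 | Level 3 | 50 × 50 = 2,500 |
| one of each | none | 2 × 20 × 50 = 2,000 |

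The unclassified pairs are exactly the mixed ones. This counts grid cells, not patients.

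**2. Add a third draw to a mixed pair.**

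- below 3: still no level
- 3.0–4.9: Level 2
- 5.0–9.9: Level 3
- 10 or more: Level 4

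So the gap closes at the next value of at least 3 × ULN. The loss is the time between the second and third draws: 4 weeks up to Week 56 and 12 weeks afterwards, unless the investigator orders a test sooner.

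**3. Ceiling on the number affected.** Only a patient with a value of at least 5 × ULN can fall into the gap. The nearest rate in the protocol is 4 of 29 adults with ALT above 5 × ULN (Section 2.6.3), and planned enrolment is about 45 (Section 12.1.2).

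- 45 × 4/29 = 6.2 patients
- Exact 95% interval for 4/29: 3.9% to 31.7%, that is 45 × 0.039 = 1.8 to 45 × 0.317 = 14.2 patients

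This is before removing patients with two values of at least 5 or any value of at least 10.

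**4. Share of those whose two draws straddle 5 × ULN.** The protocol gives no within-patient variability, so this step is an assumption: independent lognormal draws around a constant median *m*, with within-patient CV *c* and log-scale SD σ = √ln(1 + *c*²). Let *a* = P(3 ≤ X < 5) and *b* = P(5 ≤ X < 10). Given both draws in 3–10 and at least one of 5 or more,

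P(straddle) = 2*ab* / (2*ab* + *b*²) = 2*a* / (2*a* + *b*).

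For *c* = 25%, σ = 0.246; at *m* = 5, *a* = 0.481 and *b* = 0.498, giving 0.962 / (0.962 + 0.498) = 66%.

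| True level (× ULN) | CV 25% | CV 15–35% |
|---|---|---|
| 4 | 88% | 81–96% |
| 5 | 66% | 64–67% |
| 6 | 38% | 20–46% |
| 7 | 17% | 2–31% |

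**5. Still unclassified after one more draw.** With *t* = P(X < 3), the share of all pairs within 3–10 that straddle and then have a third value below 3 is 2*ab* × *t* / (*a* + *b*)². For true levels 4 to 6 and CV 15–35% it runs from 0% to 9%.

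**6. After rewording.** With Level 2 as at least 3 × ULN twice and not meeting Level 3 or 4, the 2,000 mixed pairs join Level 2 (400 + 2,000 = 2,400). Level 3 stays at 2,500 and no pair is unclassified.

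**The case against.** The literal gap is hard to dispute; the case against concerns its importance.

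- **A mandatory sentence exists.** The synopsis says the dose will be reduced for enzyme elevations above prespecified thresholds. But those thresholds are the levels in Section 7.3.2, so the sentence leads back to the gap.
- **The biopsy paragraph shows the intended reading.** It does suggest the cap is unintended. It governs biopsy only, however, and conflicts with the operative definition of Level 2.
- **No patient has a required retest after a single raised value.** True: the patient at 4.0 and 4.0 waits just as long for the second draw, and the rewording does not shorten that wait. What it changes is what follows the second draw.
- **The affected group is narrower than the ceiling.** This stands. Nausea, vomiting and abdominal pain are common on this drug and, with raised enzymes, trigger discontinuation. If the other enzyme is 3.0–4.9 on both draws, Level 2 is met through it. Three of the four adults above 5 × ULN reported alcohol intake over the protocol limit, so the rate in children may be lower.
- **Other safeguards exist.** Any value of at least 5 × ULN is an AESI on a single draw, reportable within 15 days (Sections 11.1.6 and 11.5.2), and "All AESIs will be diligently followed-up using specialised query follow-up forms". The investigator or DSMB may reduce or stop the drug, unscheduled visits are possible, and Section 12.3.6 also plans shift tables and listings. These limit the harm, but none fixes a dose step or a retest interval for this patient.
- **The summary rule may be settled in the SAP.** Possibly, but the levels themselves are fixed in the protocol, and a table built on them inherits the gap.
- **Calling 4.5 then 9.0 Level 2 could steer sites to reduce rather than interrupt.** Today nothing is required, so Level 2 is a floor, and the discretion to interrupt remains.

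**Conclusion.** The concern holds. As written, the rule requires less of a worsening patient than of a stable one with lower values, and no other text in the protocol closes the gap. It should be corrected, but its practical reach is limited. At most about 6 of 45 patients could be exposed on the adult rate (limits about 2 to 14), fewer once symptomatic patients and those with two values of at least 5 or one of at least 10 are removed. The consequence is mainly a delay of 4 or 12 weeks in required action, not permanent omission.

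The definitional gap rests on no assumption beyond the stated scope. The ceiling assumes the adult rate carries over to children. The straddle shares depend on an assumed variability model and range from 2% to 96%, so they show that mixed pairs are plausible near 5 × ULN, not how often they will occur.

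**What to change.** In Section 7.3.2, define Level 2 as ALT or AST of at least 3 × ULN on two separate occasions at least 7 days apart, not meeting Level 3 or Level 4. Leave Level 3 and the single-draw Level 4 criterion unchanged. Use the same definition for the summary by level in Section 12.3.6. This also brings Level 2 into line with the uncapped wording of the biopsy paragraph.

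The text change is one phrase, submitted as an amendment under Section 15. In practice slightly more patients will be counted as Level 2 and have their dose reduced.
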